**5.3.6.2      Exploratory Research Variables and Validation Studies**

Optional samples may be collected to conduct exploratory investigations into known and novel biomarkers. The types of biomarkers to be analyzed may include, but are not limited to nucleic acids, proteins, lipids, or metabolites.

Genetic (DNA and RNA) exploratory research will be restricted to the subject's response to treatment in terms of pharmacokinetics, efficacy, tolerability and safety.

The serum and plasma biomarker samples may be analyzed as part of a multi-study assessment of factors influencing the subjects' response to the study drug (or drugs of the same or similar class) or the development and progression of the subjects' disease or related conditions. The samples may also be used to develop new diagnostic tests, therapies, research methods or technologies.

Biomarker assessments may be used to assess and generate prognostic, predictive, pharmacodynamic, or surrogate biomarker signatures. These assessments may be explored in the context of RA or related conditions and/or upadacitinib or drugs of similar classes. The results from genetic and biomarker analyses are exploratory in nature and may not be included with the clinical study report (CSR).

**5.4 Removal of Subjects from Therapy or Assessment****5.4.1 Discontinuation of Individual Subjects**

Subjects can request to be discontinued from participation in the study at any time for any reason, including but not limited to disease progression or lack of response to treatment. The Investigator may discontinue any subject's participation for any reason, including an AE, safety concerns, lack of efficacy, or failure to comply with the protocol. See Section 6.1.7 for toxicity management criteria.

Subjects will be withdrawn from the study immediately if any of the following occur:

- Clinically significant abnormal laboratory results or AEs, which rule out continuation of the study drug, as determined by the Investigator or the AbbVie TA MD.
- Serious infections (e.g., sepsis) which cannot be adequately controlled within 2 weeks by anti-infective treatment or would put the subject at risk for continued participation in the trial as determined by the Investigator.
- The Investigator believes it is in the best interest of the subject.
- The subject requests withdrawal from the study.
- Inclusion or exclusion criteria violation was noted after the subject started study drug, when continuation of the study drug would place the subject at risk as determined by the AbbVie TA MD.
- Introduction of prohibited medications or dosages when continuation of the study drug would place the subject at risk, as determined by the AbbVie TA MD.
- Subject is non-compliant with TB prophylaxis (if applicable) or develops active TB at any time during the study.
- The subject becomes pregnant while on study drug.
- Malignancy, except for localized NMSC or carcinoma in situ of the cervix.
- Subject is significantly non-compliant with study procedures which would put the subject at risk for continued participation in the trial as determined by the Investigator.

- Subject develops a gastrointestinal perforation.
- Starting at Week 24, at least 20% improvement in BOTH TJC and SJC compared to baseline is required to remain in the study. Anyone who does not fulfill this criterion at 2 consecutive visits (starting at Week 24) must be discontinued from the study.
- If a subject is unblinded in Period 1, as summarized in Section [5.5.5](#).

If a subject prematurely discontinues study drug treatment and study participation (withdrawal of informed consent), the procedures outlined for the Premature Discontinuation visit (PD Visit) should be completed as soon as possible, preferably within 2 weeks. A 30-day follow-up visit/phone call may occur for subjects who prematurely discontinued from study drug and study participation to determine the status of any upadacitinib ongoing AEs/SAEs or the occurrence of any new AEs/SAEs (refer to Section [5.1](#) regarding Follow-Up Visit). Subjects who discontinue the study prematurely after randomization will not be replaced.

All attempts must be made to determine the date of the last study drug dose and the primary reason for discontinuation of study participation. The information will be recorded on the appropriate eCRF page. However, these procedures should not interfere with the initiation of any new treatments or therapeutic modalities that the Investigator feels are necessary to treat the subject's condition. Following discontinuation of study drug, the subject will be treated in accordance with the Investigator's best clinical judgment.

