### **Premature Discontinuation of Study (Withdrawal of Informed Consent)**

Subjects may withdraw from the study (withdrawal of informed consent) for any reason at any time (refer to Section 5.4.1 for additional details). If a subject prematurely discontinues study drug treatment and study participation (withdrawal of informed consent), the procedures outlined for the Premature Discontinuation visit (PD visit) should be completed as soon as possible, preferably within 2 weeks of study drug discontinuation.

In addition, if the subject is willing, a 30-day follow-up visit (or phone call if a visit is not possible) may occur to determine the status of any ongoing AEs/SAEs or the occurrence of any new AEs/SAEs.

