### **Follow-Up Period**

A Follow-Up Visit will occur approximately 30 days after the last dose of study drug to obtain information on any new or ongoing AE/SAEs, and to collect vital signs and clinical laboratory tests.

Subjects will complete the 30 day-Follow-Up Visit when they have either:

- Completed the last visit of Period 1 (Week 12), but decided not to participate in Period 2; OR
- Completed the last visit of Period 2; OR

- Prematurely discontinued study drug and study participation. If a Premature Discontinuation visit has already occurred, then the 30 day Follow-Up visit may be a telephone call if a site visit is not possible.

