- l. A urine pregnancy test will be performed for all women of childbearing potential at the Baseline Visit prior to the first dose of study drug and all subsequent visits except Week 1. In Period 2, for women of childbearing potential, a urine pregnancy test will be performed at all visits, including the 30 days follow-up visit, and starting at Week 24 a urine pregnancy test will be performed monthly at home between scheduled study visits. If the baseline urine pregnancy test performed at the site is negative, then dosing with study drug may begin. If the baseline or post-baseline urine pregnancy test performed at the site is positive, dosing with study drug must be withheld and a serum pregnancy test is required. The serum pregnancy test will be sent to and performed by the central laboratory. If the serum pregnancy test is negative, study drug may be started or resumed. If the serum pregnancy test is positive, study drug must be withheld and the subject must be discontinued from the study. In the event a pregnancy test comes back borderline, a repeat test is required ( $\geq 3$  days later) to document continued lack of a positive result. If during the course of the study a woman becomes surgically sterile or post-menopausal and complete documentation as described in Section 5.2.4 is available, pregnancy testing is no longer required.

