#### **6.1.4 Adverse Event Collection Period**

All AEs reported from the time of study drug administration until 30 days following discontinuation of study drug administration have elapsed will be collected, whether solicited or spontaneously reported by the subject. In addition, SAEs and protocol-related nonserious AEs will be collected from the time the subject signed the study-specific informed consent.

Adverse event information will be collected as shown in [Figure 4](#).

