Activity	Wk				Wk 16 20	Wk 24	Wk 36	Wk 48	Monthly	Every 12 Weeks Until Study Completion ^a	Every 24 Weeks Until Study Completion ^a	Every 48 Weeks Until Study Completion ^a	Final/ PD Visit	30-Day F/U Visit/ Call ^b	
	Wk	Wk	Wk	Wk											
In-home urine pregnancy test ^m									X						
Central lab tests	X	X	X	X						X					
hsCRP ⁿ															
Blood chemistry ^o															
Hematology (CBC)															
Urinalysis ^p															
ESR (local lab)	X	X	X	X						X					X
HBV screening ^q			X	X						X					
In vivo pharmacodynamic biomarkers			X	X						X					
Dispense study drug and subject dosing diary	X	X	X	X						X					
Review and retain a copy subject dosing diary and perform drug reconciliation	X	X	X	X						X					X

BL = Baseline Visit; CBC = complete blood count; csDMARD = conventional synthetic disease-modifying anti-rheumatic drug; ECG = electrocardiogram; F/U = Follow-up; HAQ-DI = Health Assessment Questionnaire – Disability Index; hsCRP = high-sensitivity C-reactive protein; NRS = numerical rating scale; PDD = Prenature Discontinuation; PhGA = Physician's Global Disease Activity; PPD = purified protein derivative; PtGA = Patient's Global Assessment of Disease Activity; RCT = randomized controlled trial; SAE = serious adverse event; SJC = Swollen Joint Count; TB = tuberculosis; TJC = Tender Joint Count; VAS = visual analog scale; Wk = Week

- a. Every 12, 24, or 48 weeks from the Week 48 visit.
- b. This visit is 30 days after last close of study drug for those subjects who complete Period 2. A 30-day follow-up phone call should also be performed for subjects who have completed PD visit to determine the status of any ongoing AEs/SAEs or the occurrence of any new AEs/SAEs.

Table 3. Studies Activities (Period 2) (Continued)

- c. At Week 24 (after Week 24 assessments have been performed), if a subject fails to meet LDA criterion (LDA defined as CDAI ≤ 10) investigator should adjust the subject's background RA therapies. Initiation of or change in corticosteroids, NSAIDs, acetaminophen, or adding or increasing doses of csDMARDs (concomitant use of up to 2 csDMARDs except the combination of MTX and leflunomide; see Inclusion Criterion 3) is allowed as per local label.
- d. Prior to other procedures. For morning stiffness, duration will be captured only if NRS rating is > 0 .

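### The 30-day follow-up of subjects who stop early is mandatory in some parts of the protocol and optional in others, although AE collection and the TEAE window both run to 30 days

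*Protocol*

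**What the plan says.** **Required or assigned.** Protocol 5.1, Follow-Up Period: "Subjects will complete the 30 day-Follow-Up Visit when they have either" one of three conditions is met. The third condition is having stopped both study drug and participation early. If a PD visit has already taken place, "then the 30 day Follow-Up visit may be a telephone call if a site visit is not possible"; this relaxes how the contact is made, not whether it is made. The notes to Figures 1 and 2, Table 2 note c and Table 4 note b also name early stoppers among those for whom the follow-up is intended. The table notes then allow a telephone call after a PD visit.

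**Optional.** Protocol 5.1, Premature Discontinuation of Study: "In addition, if the subject is willing, a 30-day follow-up visit (or phone call if a visit is not possible) may occur". Protocol 5.4.1: "A 30-day follow-up visit/phone call may occur for subjects who prematurely discontinued from study drug and study participation".

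**SAP 4.2.** The Premature Discontinuation text makes a telephone call optional and dependent on willingness. The Follow-Up Visit text requires the contact. Table 3 note b says "A 30-day follow-up phone call should also be performed for subjects who have completed PD visit".

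**Observation window.** Protocol 6.1.4: "All AEs reported from the time of study drug administration until 30 days following discontinuation of study drug administration have elapsed will be collected". Protocol 8.1.5.2.1 and SAP 10.2.1 use the same 30 days after the last dose to define a treatment-emergent event.

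**What the visit contains.** The Follow-Up Period text lists AE information, vital signs and laboratory tests. For women of childbearing potential in Period 2, Table 5 note l adds that "a urine pregnancy test will be performed at all visits, including the 30 days follow-up visit".

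**The concern.** The safety analysis counts events up to 30 days after the last dose. For subjects who stop early, the protocol does not say consistently whether anyone must contact them after the PD visit. A site relying on the optional sentences could reasonably treat that visit as the last contact.

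These are the subjects in whom late events matter most, because 5.4.1 covers removals for toxicity as well as voluntary departures. An event that is never elicited leaves no trace in the analysis. It is absent from the count of treatment-emergent events, the exposure denominator does not change, and SAP 10.1 does not impute missing safety data.

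**Working it through.** The protocol gives no figure to reproduce. The check is a comparison of text plus one subtraction.

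**Step 1: do the rules concern the same subjects?** The third condition in the Follow-Up Period text and the optional sentence in 5.4.1 describe the same group, those who stop both drug and participation early. One makes the contact obligatory and the other permits it. They cannot both be the rule.

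**Step 2: does the cross-reference settle it?** The 5.4.1 sentence ends by referring the reader to 5.1 for the Follow-Up Visit. Section 5.1 contains both the mandatory text (Follow-Up Period) and the optional text (Premature Discontinuation), so the conflict remains.

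**Step 3: is the optional wording confined to withdrawal of consent?** In 5.1 the heading carries that parenthesis. In 5.4.1 the parenthesis is attached to the preceding sentence, on the PD visit. The follow-up sentence does not repeat it, and the paragraph comes directly after the list of grounds for immediate withdrawal. The subject's own request is only one of those grounds. Others are adverse events or laboratory results that rule out continuing, uncontrolled serious infection, malignancy, gastrointestinal perforation, pregnancy and the 20% joint-count rule. No separate follow-up rule is given for these subjects.

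**Step 4: how much of the window can lack a scheduled contact?**
- Window: 30 days after the last dose (Protocol 6.1.4 and 8.1.5.2.1; SAP 10.2.1).
- PD visit: preferably within 2 weeks, i.e. 14 days, of stopping drug (Protocol 5.1).
- Days without scheduled contact = 30 − day of PD visit, if that visit is the last contact.
- PD visit on day 14: 30 − 14 = 16 days; 16/30 = 53%.
- PD visit on day 1: 30 − 1 = 29 days; 29/30 = 97%.

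The 14-day limit is a preference. A later PD visit would leave fewer than 16 days.

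**Step 5: effect on the long-term rates.** SAP 10.2.3 divides the number of treatment-emergent events by years of exposure. Protocol 8.1.2.3 ends exposure at the last dose. A missed event after treatment therefore lowers the numerator only.

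**Step 6: how many subjects?** This cannot be derived. The 5% drop-out in Protocol 8.2 is a sample-size allowance and is not split by reason. No discontinuation rate is given for Period 2.

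**The case against.** The strongest reply is that the protocol, read as a whole, already requires the contact. The dedicated Follow-Up Period text is mandatory, the figure notes and both schedule footnotes include early stoppers, and 5.4.1 points to 5.1. On this view the optional sentences are outliers written for subjects who withdraw consent, whose follow-up cannot be compelled. Much of this stands. It would be wrong to infer that the follow-up is required in only one place, and the willingness condition is appropriate for consent withdrawal. The reply does not remove the conflict, because 5.4.1 extends the optional wording to subjects who have not withdrawn consent.

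A second reply is that other text protects the data, and this also stands in part. Protocol 6.1.4 covers events reported within 30 days, solicited or spontaneous. Section 6.1 requires all AEs to be followed to a conclusion. Sections 5.3.1.1 and 6.1.7 require clinically significant laboratory abnormalities to be followed to resolution. Section 6.1.6 collects pregnancies through 30 days after the last dose. A reader might infer that laboratory recovery and pregnancy go unchecked in early stoppers; these sections do not support that. None of them, however, guarantees a contact at which a new late event would be asked about.

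Third, the SAP (version 1.0, 31 August 2017) predates the current protocol synopsis (23 February 2018) and does not direct sites. Its wording is therefore secondary evidence. The conflict stands on the protocol alone.

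**Conclusion.** The inconsistency is real and lies in the current operative text of the protocol. Its consequence is limited: new events arising between the PD visit and day 30 may go unsolicited in subjects who stop early, including those removed for toxicity. If the PD visit takes place within the preferred 14 days and no later contact follows, at least 16 of the 30 days (53%) have no scheduled contact, rising to 29 days (97%) with a PD visit on day 1.

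Two stronger readings are not supported. A reader might project a count of affected subjects from the 5% drop-out allowance or from the roughly three and a half years of dosing mentioned in 5.6.4. Neither gives the number who stop for reasons other than consent withdrawal and then receive no contact. A reader might also infer that ascertainment will differ between doses. That would require stopping to be dose-related and sites to follow the optional wording, and the documents establish neither.

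**What to change.** Reconcile the Protocol 5.1 Premature Discontinuation and Follow-Up Period texts, 5.4.1, Table 2 note c and Table 4 note b so that the 30-day follow-up has one stated status, consistent with the collection period in 6.1.4. The wording should distinguish withdrawal of consent from the other early stops listed in 5.4.1. Align SAP 4.2 (Premature Discontinuation, Follow-Up Visit and Table 3 note b) with the result.

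The sponsor should also reconcile the telephone option with the laboratory and pregnancy tests listed for that visit, since a call cannot deliver them as written. How to do so is for the sponsor to decide.

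The cost is an amendment to wording, plus some contacts with early stoppers that the schedule already provides for.

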### **Lost to Follow-Up**

For subjects to be considered lost to follow-up, reasonable attempts must be made to obtain information on the final status of the subject. At a minimum, two phone calls must be made and one certified letter must be sent and documented in the subject's source documentation.

---

**5.4.2 Discontinuation of Entire Study**

AbbVie may terminate this study prematurely, either in its entirety or at any study site, for reasonable cause provided that written notice is submitted in advance of the intended termination. The Investigator may also terminate the study at his/her site for reasonable cause, after providing written notice to AbbVie in advance of the intended termination. Advance notice is not required by either party if the study is stopped due to safety concerns. If AbbVie terminates the study for safety reasons, AbbVie will immediately notify the Investigator by telephone and subsequently provide written instructions for study termination.

**5.5 Treatments****5.5.1 Treatments Administered**

Study drug will be taken orally once daily, beginning on Day 1 (Baseline), and should be taken at approximately the same time each day. The study drug can be taken with or without food. Subjects will continue their stable therapy of csDMARD. AbbVie will not supply csDMARD(s) (nor folic acid or equivalent, such as folinic acid, for subjects who are on MTX).

**5.5.2 Identity of Investigational Product**

The individual study drug information is presented in [Table 6](#).

**Table 6. Identity of Investigational Product**

Investigational Product	Mode of Administration	Formulation	Strength	Manufacturer
Upadacitinib	Oral	Tablet (extended-release)	7.5mg 15 mg 30 mg	[REDACTED]
Matching placebo	Oral	Tablet	NA	[REDACTED]

### **5.5.2.1 Packaging and Labeling**

Upadacitinib and matching placebo will be packaged in bottles with quantities sufficient to accommodate study design. Each kit label will contain a unique kit number. This kit number is assigned to a subject via IRT and encodes the appropriate study drug to be dispensed at the subject's corresponding study visit. Each kit will be labeled as required per country requirements. Labels must remain affixed to the kits. All blank spaces on the label will be completed by the site staff prior to dispensing to the subjects.

### **5.5.2.2 Storage and Disposition of Study Drugs**

Upadacitinib must be stored at controlled room temperature (15° to 25°C/59° to 77°F). The investigational products are for investigational use only and are to be used only within the context of this study. The study drug supplied for this study must be maintained under adequate security and stored under the conditions specified on the label until dispensed for subject use or destroyed on site as appropriate.

### **5.5.3 Method of Assigning Subjects to Treatment Groups**

All subjects will be randomized using IRT. Before the study is initiated, IRT directions will be provided to each site.

All subjects will be assigned a unique identification number by the IRT at the Screening Visit. For subjects that re-screen, the Screening number assigned by the IRT at the initial Screening visit should be used; a new Screening number should not be requested.

Subjects will be eligible for randomization if they continue to meet all of the selection criteria (Section 5.2) at Baseline and are willing to continue in the study.

Subjects will be randomized in a 3:3:3:1:1:1 ratio using interactive response technology (IRT) to receive double-blind study drug in one of the following treatment groups:

- Group 1: upadacitinib 7.5 mg QD (N = 48) (Period 1) → upadacitinib 7.5 mg QD (Period 2)

- Group 2: upadacitinib 15 mg QD (N = 48) (Period 1) → upadacitinib 15 mg QD (Period 2)
- Group 3: upadacitinib 30 mg QD (N = 48) (Period 1) → upadacitinib 30 mg QD (Period 2)
- Group 4: Placebo (N = 16) (Period 1) → upadacitinib 7.5 mg QD (Period 2)
- Group 5: Placebo (N = 16) (Period 1) → upadacitinib 15 mg QD (Period 2)
- Group 6: Placebo (N = 16) (Period 1) → upadacitinib 30 mg QD (Period 2)

Randomization will be stratified by prior exposure to bDMARD (yes/no).

The IRT will assign a randomization number that will encode the subject's treatment group assignment according to the randomization schedule generated by the Statistics Department at AbbVie.

IRT will provide the appropriate study drug kit number(s) to dispense to each subject. Study drug will be administered at the study visits as summarized in Section 5.3.1.1. Returned study drug should not be re-dispensed to any subject.

#### **5.5.4 Selection and Timing of Dose for Each Subject**

Subjects should take study drug as outlined in Section 5.5.1.

On dosing days that occur on study visit days, subjects should follow the regular dosing schedule (refer to Section 5.3.2.1 regarding Week 1 and Week 2 visits).

Each subject's dosing schedule should be closely monitored by the site at each study visit by careful review of the subject's dosing diary. This will ensure that all subjects enrolled into the study maintain their original dosing schedule beginning with the first dose of study drug (Baseline/Day 1).

If a subject should forget to take their upadacitinib (or matching placebo) dose at their regularly scheduled dosing time, they should take the forgotten dose as soon as they remember the dose was missed as long as it is at least 10 hours before their next scheduled

dose. If a subject only remembers the missed dose within 10 hours before next scheduled dose, the subject should skip the missed dose and take the next dose at the scheduled time. If the subject experiences a study drug interruption > 7 consecutive days during Weeks 1 through 24 or > 30 consecutive days after Week 24 (other than for reasons listed in Section 6.1.7), they should notify their study site physician, and the subject should be discontinued from the study.

